4.6.1	Adverse Events and Serious Adverse Events	20
4.6.2	Other Safety Variables	20
4.7	Analysis of Other Variables	21
4.7.1	Other Efficacy Variables 1.....	21
4.7.2	Other Efficacy Variables 2.....	21
5	Changes to the Protocol Defined Statistical Analysis Plan.....	22
	Attachment 1: List of Data Displays.....	22

List of tables

Table 1-1	Schedule of Activities	7
------------------	-------------------------------------	----------

Abbreviations

Abbreviation	Term
AEs	Adverse Events
ANCOVA	Analysis Of Covariance
BDRM	Blinded Data Review Meeting
CIs	Confidence Intervals
DH	Dental Hypersensitivity
DHEQ	Dental Hypersensitivity Experience Questionnaire
eCRF	Electronic Case Report Form
GSKCH	GlaxoSmithKline Consumer Healthcare
ICF	Informed Consent Form
IP	Investigational Product
KNO ₃	Potassium Nitrate
MedDRA	Medical Dictionary for Regulatory Activities
miITT	Modified Intent-To-Treat
N/A	Not Applicable
OHRQoL	Oral Health Related Quality of Life
OHT	Oral Hard Tissue
OST	Oral Soft Tissue
PDMP	Protocol Deviation Management Plan
PP	Per Protocol
PT	Preferred Term
RAP	Reporting and Analysis Plan
SAE	Serious Adverse Events
SE	Standard Error
SD	Standard Deviation
SMFP	Sodium Monofluorophosphate
SnF ₂	Stannous Fluoride
SOC	System Organ Class
TEAE	Treatment Emergent Adverse Event

The purpose of this Statistical Reporting and Analysis Plan (RAP) is to describe the planned analyses and outputs to be included in the Clinical Study Report for Protocol 209723 v2.0 dated 16 Oct 2018.

1 Summary of Key Protocol Information

GlaxoSmithKline Consumer Healthcare (GSK CH) has developed an anhydrous 5% potassium nitrate (KNO_3) and 0.454% stannous fluoride (SnF_2) combination dentifrice for the relief of dentin hypersensitivity (DH). It is hypothesized that the combination of two anti-sensitivity active ingredients with complementary modes of action (KNO_3 : nerve desensitization; SnF_2 : dentin tubule occlusion) will deliver superior anti-sensitivity efficacy, compared to either active alone. Published clinical studies report DH efficacy for $\text{KNO}_3/\text{SnF}_2$ combination dentifrices and indicate greater clinical benefit for dual active formulations, compared to KNO_3 only formulations, with 4-8 weeks treatment. They do not provide any information regarding performance versus SnF_2 only formulations (no SnF_2 only dentifrices were evaluated). This exploratory study will characterize the efficacy profile of an experimental 5% KNO_3 and 0.454% SnF_2 combination dentifrice, compared to a 0.454% SnF_2 single active desensitizing dentifrice, across an 8-week treatment period.

1.1 Study Design

This will be a single center, 8-week, randomized, controlled, examiner-blind, two treatment arm, parallel design, stratified (by maximum Baseline Schiff sensitivity score of the two selected test teeth), Phase II, exploratory study to evaluate the DH efficacy of an experimental 5% KNO_3 and 0.454% SnF_2 combination dentifrice (Test), compared to a marketed 0.454% SnF_2 desensitizing dentifrice (Control). Study dentifrices will be applied twice daily, by tooth brushing, over the 8-week treatment period.

DH to tactile and evaporative air stimuli will be assessed at Screening (Visit 1) and Baseline (Visit 2), and after 3, 7, 14, 28 and 56 days treatment (Visits 3-7). Eligible subjects will complete an acclimatization phase (2-4 weeks) between the Screening and Baseline visits and will be randomized to study dentifrice following Baseline assessments. The safety and oral tolerability of the study products will be monitored over the treatment period by review of reported adverse events (AEs).

5% Potassium Nitrate and 0.454% Stannous Fluoride Combination Dentifrice

209723

Final Statistical Reporting and Analysis Plan Amendment v1.0, 27 Sep 2019

Table 1-1 Schedule of Activities

Procedure/ Assessment	Visit 1 Day -28 to -14 Screening	Visit 2 Day 0 Baseline	Visit 3 Day 3	Visit 4 Day 7 (+1day)	Visit 5 Day 14 (±1day)	Visit 6 Day 28 (±2days)	Visit 7 Day 56 (±2days)
Informed Consent	X						
Demographics	X						
Medical History	X						
Prior/Current Medications and Treatments	X						
Review Subject's Current Oral Care Products	X						
Subject Returns with Acclimatization Dentifrice, Toothbrush and Completed Diary ¹		X					
Subject Returns with Study Treatment, Toothbrush and Completed Diary ¹			X	X	X	X	X
Compliance Checks ²		X	X	X	X	X	X
Concomitant Medications and Treatments		X	X	X	X	X	X
Urine Pregnancy Test (UPT) ³	X						
Subject Continuance			X	X	X	X	X
Dentine Hypersensitivity Experience Questionnaire (DHEQ) ⁴		X				X	X
Oral Soft Tissue (OST) Examination	X					X	X
Oral Hard Tissue (OHT) Examination	X						X
Eligible Teeth Assessments (Dentition Exclusions, Erosion/Abrasion/Recession [EAR], Modified Gingival Index [MGI], Tooth Mobility)	X						

Procedure/ Assessment	Visit 1 Day -28 to -14 Screening	Visit 2 Day 0 Baseline	Visit 3 Day 3	Visit 4 Day 7 (+1day)	Visit 5 Day 14 (±1day)	Visit 6 Day 28 (±2days)	Visit 7 Day 56 (±2days)
Qualifying Tactile Sensitivity Assessment (Tactile Threshold) ⁵	X	X					
Qualifying Evaporative Air Sensitivity Assessment (Schiff sensitivity score) ⁶	X	X					
Inclusion / Exclusion Criteria	X	X					
Subject Eligibility	X	X					
Clinical Examiner Selects Two 'Test Teeth' Eligible Subjects Only		X					
Stratification/Randomization		X					
Dispense Acclimatization dentifrice, Toothbrush, Diary and Timer	X						
Supervised Brushing with Acclimatization Dentifrice	X						
Dispense Study Treatment, Toothbrush and Diary		X					
Tactile Sensitivity Assessment (Yeaple Probe) ⁵ Test Teeth Only		X	X	X	X	X	X
Evaporative Air Sensitivity (Schiff sensitivity score) ⁶ Test Teeth Only		X	X	X	X	X	X
Evaporative Air Sensitivity (Schiff sensitivity score) ⁶		X	X	X	X	X	X
Remaining Eligible Teeth from Screening							
Supervised Brushing with Study Treatment		X	X	X	X	X	
Return Study Treatment/Toothbrush and Diary to Subject			X	X	X	X	
Adverse Events/Incidents ⁷	X	X	X	X	X	X	X
Study Conclusion							X

Footnotes:

1. Subject will be required to bring their study supplies (minus timer) to every visit.
2. Perform visual check of returned study supplies and review diary (Visit 2: compliance with use of acclimatization dentifrice; Visits 3-7: compliance with use of study treatment). Check compliance with Lifestyle Guidelines/Medication Requirements.
3. Female subjects of child bearing potential only.
4. DHEQ must be completed prior to OST examination/clinical assessments.
5. Visits 1-2: maximum force 20 g (Screening and Baseline); Visits 3-7: maximum force 80 g.
6. Evaporative air assessment will follow tactile assessment, with minimum 5 minutes between last tactile assessment and first evaporative (air) assessment (to allow tooth recovery). Visits 3-7: Complete evaporative (air) assessments for 2 test teeth first, before assessing remaining eligible teeth from Screening.
7. AEs, and therefore all Serious Adverse Events (SAEs), and incidents will be recorded from immediately after a subject consents to participate in the study (by the completion of the Informed Consent Form [ICF]) until 5 days after last dose of study treatment.

1.2 Study Objectives

Objectives	Endpoints
Primary	
To characterize the efficacy profiles of an experimental 5% w/w KNO ₃ and 0.454% w/w SnF ₂ combination dentifrice and a 0.454% w/w SnF ₂ only dentifrice in reducing DH, with twice daily use for 8 weeks.	At Baseline, Days 3, 7, 14, 28, 56; Schiff sensitivity score Tactile threshold (grams [g]) Number of sensitive teeth (Schiff sensitivity score ≥ 1)
Secondary	
To investigate the clinical efficacy of an experimental 5% w/w KNO ₃ and 0.454% w/w SnF ₂ combination dentifrice in reducing DH to an evaporative air stimulus (Schiff sensitivity score), compared to a 0.454% w/w SnF ₂ only dentifrice, after 8 weeks twice daily use.	Change from Baseline in Schiff sensitivity score at Day 56
To investigate the clinical efficacy of an experimental 5% w/w KNO ₃ and 0.454% w/w SnF ₂ combination dentifrice in reducing DH to a tactile stimulus (tactile threshold), compared to a 0.454% w/w SnF ₂ only dentifrice, after 8 weeks twice daily use.	Change from Baseline in tactile threshold (g) at Day 56
Safety	
To assess the safety and tolerability of an experimental 5% w/w KNO ₃ and 0.454% w/w SnF ₂ combination dentifrice with twice daily use for 8 weeks.	Treatment emergent adverse events
Other	
To investigate the clinical efficacy of an experimental 5% w/w KNO ₃ and 0.454% w/w SnF ₂ combination dentifrice in reducing DH to evaporative air (Schiff sensitivity score) and tactile (tactile threshold) stimuli, compared to a 0.454% w/w SnF ₂ only dentifrice, after 3, 7, 14 & 28 days twice daily use.	At Days 3, 7, 14 & 28; Change from Baseline in Schiff sensitivity score Change from Baseline in tactile threshold (g)
To monitor Oral Health Related Quality of Life (OHRQoL) as measured by the Dentine Hypersensitivity Experience Questionnaire (DHEQ) after 4 and 8 weeks treatment with an experimental 5% w/w KNO ₃ and 0.454% w/w SnF ₂ combination dentifrice and a 0.454% w/w SnF ₂ only dentifrice.	At Days 28 & Day 56; Change from Baseline in 
 - responses to Questions 7-9, DHEQ Section 1 - Total Score, Questions 1-15, DHEQ Section 2 - Restrictions, Adaptation, Social Impact, Emotional Impact & Identity Domains

1.3 Treatments

	Acclimatization Dentifrice	Test Dentifrice	Control Dentifrice
Treatment Description	Dentifrice containing 1000 parts per million (ppm) fluoride as sodium monofluorophosphate (SMFP)	Dentifrice containing 5% w/w KNO_3 and 0.454% w/w SnF_2 (1100 ppm fluoride)	Dentifrice containing 0.454% SnF_2 (1100 ppm fluoride)
Product Name	Colgate Cavity Protection (Canadian market)	Experimental dentifrice	Sensodyne Rapid Relief Regular (registered as a Non-prescription Natural Health Product [NNHP] in Canada)

Only the Test and Control dentifrices are considered to be study products.

1.4 Sample Size Calculation

No formal sample size has been produced for this exploratory clinical study to characterize the DH efficacy profile of the Investigational Product (IP), as measured by Schiff sensitivity score and tactile threshold, over time. Based on previous GSK CH studies evaluating DH efficacy of 0.454% w/w SnF_2 dentifrices, approximately 50 evaluable subjects per treatment group is considered sufficient to provide reliable estimates of treatment effect for the purposes of this study and to aid in the design of future clinical studies. Approximately 104 subjects will be randomized to study treatment (approximately 52 per treatment group) to achieve approximately 50 evaluable subjects per treatment group, allowing for a dropout rate of approximately 4%.

2 Planned Analyses

2.1 Interim Analysis

No interim analysis is planned.

2.2 Final Analyses

The final planned analyses will be performed after the completion of the following sequential steps:

-
1. All subjects have completed the study as defined in the protocol.
 2. All required database cleaning activities have been completed and database has been locked.
 3. All criteria for unblinding the randomization codes have been met and the randomization codes have been distributed.

3 Considerations for Data Analyses and Data Handling Conventions

3.1 Baseline Definition

For all endpoints, the baseline value will be the Day 0 (Visit 2) pre-treatment assessment with a non-missing value.

Unless otherwise stated, if baseline data is missing no derivation will be performed and will be set to missing.

3.2 Subgroups/Stratifications

Subgroups are not defined for this trial.

Subjects will be stratified according to the maximum Baseline Schiff sensitivity score of their two selected ‘test teeth’. The stratification factor will give rise to two strata.

- **Stratum 1:** maximum Schiff sensitivity score = 2
- **Stratum 2:** maximum Schiff sensitivity score = 3

3.3 Timepoints and Visit Windows

The time points and visits for this study are defined in [Table 1-1](#) “Schedule of Activities”. Any deviation from the study schedule will be reviewed on case-by-case basis at the Blinded Data Review Meeting (BDRM) to determine whether the data should be excluded from the Per-Protocol (PP) population.

4 Data Analysis

Data analysis will be performed by Syneos Health. Statistical analysis software SAS (Studio) version 9.4 or higher will be used.

Prior to database closure a BDRM will be conducted at which various aspects of the trial will be discussed and necessary actions, including exclusions from the Safety, modified Intent to Treat (mITT) and PP populations.

Unless otherwise described below, listings will be produced for all randomized subjects.

4.1 Populations for Analysis

Tables described in this section will be produced for all randomized subjects.

4.1.1 Subject Disposition

Subject disposition will be presented in [Table 14.1.1](#).

Subject disposition will be summarized as the number and percentage of subjects in each analysis population (defined in [Section 4.1.3](#)), who complete the study and who were discontinued from the study (by reason for discontinuation). The summary will be presented by study product and overall. The percentages will be based on the total number of subjects randomized.

Subject disposition including demographic data (age, sex, race and ethnicity), screening date, study product start date and time, study product end date and time, subject status (completer, Yes/No), study completion/withdrawal date, duration (in days) in the study (defined as [(date of completion or withdrawal minus date of signing ICF) + 1], duration (in days) of study product usage (defined as: [(date of last study product use minus date of first study product use)+1]) and the primary reason for withdrawal will be listed ([Listing 16.2.1.1](#)) by study product group.

Screen failures are defined as subjects who consent to participate in the clinical study but are not subsequently randomized. An enrolled subject is a subject who has signed informed consent and is eligible to proceed beyond the screening visit. The number of subjects screened, enrolled and randomized will be presented.

The number and percentage of screen failures with reasons why subjects were not randomized will be presented. Percentage of screen failures will be based on the total number of subjects screened.

Subject disposition information will be listed for non-randomized subjects ([Listing 16.2.1.2](#)), displaying subject number, demographic information (age, sex, race and ethnicity), screening date, reason for screen failure and any further details of reason for screen failure.

4.1.2 Protocol Deviations

Protocol deviations will be tracked by the study team throughout the conduct of the study. Data will be reviewed prior to unblinding and closure of the database to ensure all important deviations are captured and categorized. Subjects with important protocol deviations liable to influence the efficacy outcomes will be excluded from the PP population. Subjects may also be identified as having important protocol deviations not leading to exclusion from the PP population.

Important deviations from protocol procedures may include, but will not be necessarily be limited to the following:

- Consent procedures
- Inclusion/exclusion criteria
- Study procedures

The specific details of important protocol deviations will be listed in Protocol Deviation Management Plan (PDMP) and assessment process will be specified in the Blind Data Review Plan. Subjects with important protocol deviations will be identified at the BDRM.

The number and percentage of subjects with at least one important protocol deviation, with at least one important protocol deviation not leading to exclusion from PP population (with reasons for deviations) and with important protocol deviations leading to exclusion from the PP population (with reasons for deviations) will be presented in [Table 14.1.2](#) by study product and listed in [Listing 16.2.2.1](#).

Protocol deviations collected on the protocol deviation page of the electronic Case Report Form(eCRF) will be listed in [Listing 16.2.2.2](#). The listing will present date of deviation, type of deviation and deviation description.

4.1.3 Analysis Populations

Three analysis populations are defined.

Population	Definition / Criteria	Analyses Evaluated
Safety	All randomized subjects who receive at least one dose of study product. Any subject who receives a randomization number will be considered to have been randomized. This population will be based on the product the subject received.	Safety
mITT	The mITT population will include all randomized subjects who receive at least one dose of study product and have at least one post baseline efficacy measurement. Any subject who receives a randomization number will be considered to have been randomized. This population will be based on the study product to which the subject was randomized.	Efficacy

Population	Definition / Criteria	Analyses Evaluated
PP	All randomized subjects who do not have any protocol deviations that could confound the interpretation of analyses conducted on the mITT.	Efficacy
NOTES: Please refer to Attachment 1: List of Data Displays which details the population to be used for each display being generated.		

Subjects excluded from any of the analysis populations will be listed in [Listing 16.2.3.1](#).

The primary population for assessment of efficacy will be the mITT Population. A PP analysis will be performed on the primary and secondary efficacy variables if more than 10% of the subjects in the mITT Population are excluded from the PP Population. A decision on whether a PP analysis will be performed will be made prior to study unblinding (release of randomization codes).

4.2 Subject Demographics and Other Baseline Characteristics

4.2.1 Demographic Characteristics

Descriptive statistics (number of subjects (n), mean, standard deviation (SD), median, minimum and maximum for continuous variables, frequency count (n) and percentage (%) of subjects for categorical variables) will be presented for demographic variables and baseline characteristics by study product group and overall. These variables include age, gender, race, ethnicity and baseline Schiff stratification score and will be presented for the Safety population ([Table 14.1.3.1](#)) and mITT population ([Table 14.1.3.2](#)).

Demographic information will be listed ([Listing 16.2.4.1](#)) for all randomized subjects.

4.2.2 General Medical History

Medical history data will be listed ([Listing 16.2.4.2](#)) with start date and end date or ongoing at the start of study.

4.3 Treatments (Study Drug, Rescue Medication, Other Concomitant Therapies, Compliance)

Compliance data will be summarized for the mITT population. Exposure will be summarized for the Safety population. The study product kit allocations will be listed ([Listing 16.1.6.1](#)), including kit number and study product information. Randomization details will be listed ([Listing 16.1.7.1](#)), including the planned randomized study product, the actual study product received, and the randomization date.

Other concomitant therapies will be listed from all subjects from the signing of the Informed Consent Form (ICF).

4.3.1 Study Product Compliance and Exposure

Study product compliance (number of brushings/missed brushings/additional brushings) will be listed in [Listing 16.2.5.4](#) for all randomized subjects. Compliance data will be summarized for the mITT population in [Table 14.2.1](#). Total number of brushings, number of missed brushings and number of additional brushings will be summarized as separate categories in [Table 14.2.1](#).

Supervised brushings (subject number, date and time of supervised brushing, reason why supervised brushing was not performed according to the protocol) will be listed ([Listing 16.2.5.5](#)) for all randomized subjects.

4.3.2 Prior and Concomitant Medication

Medication/treatments taken within 30 days of signing the ICF will be documented as a prior medication/treatment. Medications/treatments taken after signing the ICF will be documented as concomitant medication/treatments.

Prior medications, concomitant medications and significant non-drug therapies taken during the study, from signing the informed consent, will be recorded in the eCRF. Prior and concomitant medications will be coded using an internal validated medication dictionary, GSKDrug.

Prior medications will be listed by subject, with drug name, GSK drug synonym, dose, dose form, frequency, route, start date, study day relative to study product start date and end date ([Listing 16.2.5.1](#)). Concomitant medications will be listed similarly ([Listing 16.2.5.2](#) for randomized subjects and [Listing 16.2.5.3](#) for non-randomized subjects).

Unknown dates will not be imputed. If the stop date is unknown, or incomplete, and the medication cannot be considered as stopped prior to the date of signing the ICF then the medication will be considered as a concomitant medication (unless partial start or stop dates indicate differently).

4.4 Analysis of Efficacy

The primary population for assessment of efficacy will be the mITT Population

4.4.1 Primary Efficacy Endpoints

4.4.1.1 Primary Efficacy Endpoint Definition

The primary efficacy variables are Schiff sensitivity score and tactile threshold (g), both calculated as the average score of the two test teeth, and the number of sensitive teeth

(Schiff sensitivity score ≥ 1) at Day 0 (Baseline), Day 3, Day 7, Day 14, Day 28 and Day 56.

4.4.1.2 Statistical Hypothesis, Model and Method of Analysis

No formal efficacy analysis is planned for primary endpoint.

Summary statistics (mean, median, standard error (SE), SD, minimum, maximum) will be presented for each outcome variable at each assessment time point in [Table 14.2.2.1.1](#), [Table 14.2.2.2.1](#) and [Table 14.2.2.3.1](#) for Schiff sensitivity score, tactile threshold (g) and the number of sensitive teeth respectively. Raw means (\pm SE) of the Schiff sensitivity score, tactile threshold (g) and number of sensitive teeth at each time point will be plotted by study product group in [Figure 14.2.1](#), [Figure 14.2.2](#) and [Figure 14.2.3](#) respectively.

Schiff sensitivity score and tactile threshold (g) for the two test teeth will be listed for each subject by Visit in [Listing 16.2.6.1](#) and [Listing 16.2.6.2](#) respectively. All Schiff sensitivity scores and tactile threshold (g) values recorded throughout the study will be listed by subject in [Listing 16.2.6.4](#) and [Listing 16.2.6.5](#) respectively. The number of sensitive teeth will be listed by subject in [Listing 16.2.6.3](#).

An InForm database outage occurred on 28 May 2019 that prevented the direct entry of source data from twelve (12) subjects into the InForm eCRF database. Subjects [PPD](#) [qualifying oral data \(Oral Soft Tissue \(OST\) Examination, Qualifying Tactile Sensitivity Assessment \(Tactile Threshold\) and Qualifying Evaporative Air Sensitivity Assessment \(Schiff sensitivity score\) were recorded manually on the back of the paper "Subject Source / Medical Record" document. The entries were not signed and dated. Due to this data integrity issue a sensitivity analysis will be performed to compare the results by excluding these subjects to make an inference about the study.](#)

Baseline summary statistics will be repeated for all three primary endpoints ([Table 14.2.2.1.1.1](#) for Schiff sensitivity score, [Table 14.2.2.1.1](#) for tactile threshold (g) and [Table 14.2.2.3.1.1](#) for the number of sensitive teeth) based on mITT population but excluding these 12 subjects and with only with these 12 subjects Supportive Analyses

If there is more than 10% difference in the overall number of subjects between the PP and mITT populations, a summary of the primary efficacy variables will be presented for the PP population in [Table 14.2.2.1.2](#), [Table 14.2.2.2](#) and [Table 14.2.2.3.2](#) for Schiff sensitivity score, tactile threshold (g) and the number of sensitive teeth respectively.

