4.5.1.1.2 Statistical Hypothesis, Model and Method of Analysis

Study product differences will be tested under the null hypothesis:

- H_0 : there is no treatment difference versus the alternate hypothesis;
- H_1 : there is a treatment difference

Change in Schiff sensitivity score will be analysed at Day 56 using an Analysis of Covariance (ANCOVA)model which will include study product as a factor and Baseline Schiff sensitivity score as a covariate. Note that since the Baseline Schiff sensitivity score will be included as a covariate, the Baseline Schiff stratification value will not be included in the model.

Using the above model, adjusted mean change from Baseline, along with 95% confidence intervals (CIs) will be reported by study product group. P-values testing for non-zero change from Baseline will be presented for both study product groups. Mean difference between study product groups, 95% CIs and p-values will be provided for Schiff sensitivity score in [Table 14.2.2.4.1](#). Significance testing will be conducted at the two-sided 5% significance level; no adjustment for multiple comparisons will be made.

The assumption of normality and homogeneity of variance in the ANCOVA model will be investigated, and if violated, an appropriate data transformation or non-parametric method, for example, the van Elteren test, adjusting for the maximum baseline Schiff Sensitivity scores, will be performed.

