4.5.1.1.3 Supportive Analyses

If there is more than 10% difference in the overall number of subjects between the PP and the mITT populations, a PP analysis will be performed for Secondary Efficacy Variable 1 and summarized in [Table 14.2.2.4.2](#).

4.5.1.2 Secondary Efficacy Variable 2

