4.5.1.2.2 Statistical Hypothesis, Model and Method of Analysis

Study product differences will be tested under the null hypothesis:

- H_0 : there is no treatment difference versus the alternate hypothesis;
- H_1 : there is a treatment difference

Change in tactile threshold (g) will be analysed at Day 56 using an ANCOVA model with study product and Baseline Schiff stratification included as factors and Baseline tactile threshold included as a covariate.

Using the above model, adjusted mean change from Baseline, along with 95% CIs will be reported by study product group. P-values testing for non-zero change from Baseline will be presented for both study product groups. Mean difference between study product groups, 95% CIs and p-values will be provided for tactile threshold (g) in [Table 14.2.2.5.1](#). Significance testing will be conducted at the two-sided 5% significance level; no adjustment for multiple comparisons will be made.

The assumption of normality and homogeneity of variance in the ANCOVA model will be investigated, and if violated, an appropriate data transformation or non-parametric method, for example, the van Elteren test, adjusting for the maximum baseline Schiff Sensitivity scores, will be performed.

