4.5.1.2.3 Supportive Analyses

If there is more than 10% difference in the overall number of subjects between the PP and the mITT populations, a PP analysis will be performed for Secondary Efficacy Variable 2 and summarized in [Table 14.2.2.5.2](#).

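### The sensitivity analysis promised for the 12 outage subjects stops at Baseline summaries and never reaches the Day 56 comparisons

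*SAP*

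**What the plan says.** SAP 4.4.1.2 describes a database outage on 28 May 2019. For 12 subjects the oral soft tissue (OST) examination and the qualifying tactile and Schiff assessments were recorded on the back of a paper source document, without signature or date. The SAP treats this as a data integrity issue and says that "a sensitivity analysis will be performed to compare the results by excluding these subjects to make an inference about the study".

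The next paragraph gives the outputs: "Baseline summary statistics will be repeated for all three primary endpoints", for the mITT population without the 12 and for the 12 alone. The same section says that the primary endpoints get no formal efficacy analysis.

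Formal testing is in SAP 4.5:

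- Change in Schiff score at Day 56 (4.5.1.1.2) uses an ANCOVA with "study product as a factor and Baseline Schiff sensitivity score as a covariate".
- Change in tactile threshold at Day 56 (4.5.1.2.2) uses an ANCOVA with "study product and Baseline Schiff stratification included as factors and Baseline tactile threshold included as a covariate".

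The supportive sections for these models contain one item each: "a PP analysis will be performed for Secondary Efficacy Variable 1" (4.5.1.1.3) and "a PP analysis will be performed for Secondary Efficacy Variable 2" (4.5.1.2.3). SAP 4.1.3 makes the per-protocol (PP) analysis conditional: it is run "if more than 10% of the subjects in the mITT Population are excluded from the PP Population". Protocol 3 makes a significant Day 56 Schiff difference in favour of Test its comparative criterion for success.

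**The concern.** The stated purpose and the specified output do not match. The purpose is to see whether the study's conclusion stands without 12 subjects whose records are in question. The output describes those subjects before treatment. A Baseline table carries no information on the Day 56 treatment difference, however similar or different the 12 look.

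It is also a weak check of the records. Protocol 9.2.4 admits as test teeth only those with a Baseline Schiff score of at least 2 and a tactile threshold of at most 20 g. The Schiff scale ends at 3, and the probe is calibrated in 10 g steps from 10 g. Each test tooth can therefore score only 2 or 3, and 10 g or 20 g. On these two endpoints the 12 will look much like the others whatever the quality of their records.

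The stake depends on which visit was affected. SAP 3.1 says that "the baseline value will be the Day 0 (Visit 2) pre-treatment assessment with a non-missing value". If the outage fell on Baseline visits, the unsigned values enter the change scores, both Baseline covariates, the stratum and the choice of test teeth. If it fell on Screening visits, they bear on eligibility only. In both cases the direct check is the Day 56 estimate without the 12.

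**Working it through.** **Inputs.** 12 affected subjects (SAP 4.4.1.2); about 104 randomised, 52 per arm, for about 50 evaluable per arm at about 4% dropout (SAP 1.4). The documents give no SD or effect size, so results are in units of the residual SD. Assumptions: equal arms, and all 12 in mITT with Day 56 data. The split of the 12 by arm is not stated, so a range from 6:6 to 12:0 is used.

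**The plan's own figure.** 50 / 0.96 = 52.08 per arm, which agrees with the stated 52.

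**Share of the sample.** 12/104 = 11.5%; 12/100 = 12%.

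**Loss of precision.** With *a* per arm and *x*, *y* subjects removed, SE ratio = sqrt[(1/(a−x) + 1/(a−y)) / (2/a)].

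| Split | a = 50 | a = 52 |
|---|---|---|
| 6:6 | 1.066 | 1.063 |
| 9:3 | 1.069 | 1.066 |
| 12:0 | 1.076 | 1.072 |

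The 95% CI half-width for equal arms is t × sqrt(4/n). It goes from 0.397 SD (n = 100) to 0.424 SD (n = 88), or from 0.389 SD (n = 104) to 0.414 SD (n = 92).

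**Shift expected by chance.** If the 12 do not differ from the rest, the estimate still moves when they are removed. The 95% range is ±1.96 × sqrt(variance without the 12 − variance with all). For a = 50 and 6:6 this is 1.96 × sqrt(2/44 − 2/50) = 0.145 SD.

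| Split | a = 50 | a = 52 |
|---|---|---|
| 6:6 | 0.145 SD | 0.139 SD |
| 9:3 | 0.148 SD | 0.141 SD |
| 12:0 | 0.156 SD | 0.149 SD |

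**Could the PP analysis fill the gap?** Counting these subjects alone:

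- SAP 4.1.3 needs more than 10% excluded: floor(0.1n) + 1 = 11 of the 12, at n = 100 or 104.
- Protocol 12.2.2 needs 10% or more: ceil(0.1n) = 10 at n = 100 and 11 at n = 104.

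Fewer are needed if other subjects are also excluded. However, SAP 4.1.2 leaves exclusion to the judgement of important deviations at the blinded review, and nothing says that the 12 will be excluded. A PP analysis would also drop unrelated deviators, so it would not isolate the effect of the 12.

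**Which visit?** The outage lasted one day and Screening is at least 14 days before Baseline, so at most one of each subject's two qualifying visits is affected. Two points suggest Baseline. The SAP repeats Baseline values. The list of OST, tactile and Schiff also matches Protocol 8.2.1 once Administrative Changes #02 removed the hard tissue examination from that visit. Against this, SAP Table 1-1 as extracted shows no OST examination at Visit 2, and the Protocol places its qualifying sensitivity headings under Screening (9.1). The point is open.

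**The case against.** The strongest objection is that a gap in the whole plan is not proven. SAP 4.1.3 refers to Attachment 1 for the population used in each display, and that attachment was not in the text available. A Day 56 display without the 12 could be listed there. This stands as a limit, so the finding is confined to the SAP body. But 4.4.1.2 names tables for this sensitivity analysis and none is at Day 56, while 4.5.1.1.3 and 4.5.1.2.3 mention only the PP analysis.

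A second objection is that the promise sits in the section on descriptive primary endpoints. The Baseline tables may be the whole intended analysis, with the purpose loosely worded. Narrowing the wording would remove the contradiction. It would still leave an acknowledged data integrity issue with no check on the result that decides comparative success.

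Third, the harm is small. No passage shows that any value is wrong. The assessments precede randomisation and the examiner is blinded, so bias between arms is not expected. The study is exploratory. A shift of about 0.14 to 0.16 SD can arise by chance, so the rerun will not reliably detect a problem. All of this stands. It limits the severity and governs how the result should be read, but it does not make Baseline summaries a substitute for the Day 56 estimate.

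**Conclusion.** The concern holds. As written in the SAP body, the sensitivity analysis cannot do what it is said to do: the study's inferences are the two Day 56 ANCOVAs, and neither is repeated without the 12. The only other route, the PP analysis, is conditional and does not commit to excluding them.

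The gap is modest and should be fixed. It concerns 11.5% of the planned sample, on the assumption that all 12 were randomised and are in mITT with Day 56 data. No bias between arms is expected. The figures above measure the precision of the missing check; they do not show that the Day 56 result is wrong. Confidence is medium, because Attachment 1 was not seen and the affected visit is not stated.

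**What to change.** Add to SAP 4.5.1.1.3 and 4.5.1.2.3 that the Day 56 ANCOVAs for change in Schiff score and in tactile threshold will be repeated on the mITT population without the 12 subjects, whatever is decided about the PP analysis. Report the treatment difference and 95% CI next to the main result, as a robustness check on the estimate. Do not base the reading on a p-value, and judge any shift against the 0.14 to 0.16 SD that chance alone allows. Fix the text before the randomisation codes are released, so that the choice is not made after the results are seen. A sentence in 4.4.1.2 naming the affected visit would help the reader, but the fix does not depend on it.

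The cost is two model runs and tables with a subject filter and a short SAP addition. The SE of the sensitivity estimate is about 7% larger than that of the main estimate. The main analysis is unchanged.
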